## **6.2.4 Termination criteria** (for the whole research project)

- 1) The methodology is harmful to the participants more than 20 % of participants
- 2) Researcher cannot find the patients to meet the criteria in this research

[figure not shown]
MU-CIRB	Mahidol University Central Institutional Review Board (MU-CIRB)	Date Modified 02/08/2016
Mahidol University Centra	l Institutional Review Board (MU Central-IRB) Study Protocol	Page 5 of 13

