### 6.3 Sample size

Sample size calculation will be performed using formula for the test of different between 2 independent means.

According to the G\*power 3.1.9.2 program calculation, the total of this study equal 20 subjects. Based on the previous study using the shoulder pain and disability index to measure the shoulder function, in the study of comparing the immediate effects of mobilization with movement and sham techniques. The mean (standard deviation) between group post-intervention for the mobilization with movement group was 4.6 (5.0) and that for the sham group was 0.4 (1.1) (12). In this proposed study, we need equal number of participants per group; therefore, the drop out calculation of 20% from the total participants (n = 1/1-20%). Therefore, after the ethical approval, the researcher will collect data from 24 shoulder impingement syndrome patients (12 subjects on the conventional group and 12 subjects on the mobilization with movement group).

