# - Assessment of safety

This study does not include any injection or invasive approach, or taking any medications and does not require any modification of patient treatment programs.

Before giving an informed consent, the participants will be asked whether they have any condition listed in exclusion criteria or any other conditions that may preclude participation in any aspect of the study.

The researcher will explain the procedure, purpose, advantages and possible risk of this study. The researcher will demonstrate each test prior to evaluation and will explain the procedures for each intervention. Moreover, the researcher will observe participants' feeling during assessment.

=	MU-CIRB	Mahidol University Central Institutional Review Board (MU-CIRB)	Date Modified 02/08/2016
	Mahidol University Centra	l Institutional Review Board (MU Central-IRB) Study Protocol	Page 13 of 13

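### The rule to end the trial if more than 20% are harmed has no described recording of adverse events behind it, so it cannot be applied reproducibly

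*Combined protocol and SAP*

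**What the plan says.** Section 6.2.4 sets criteria "for the whole research project", and the first is "The methodology is harmful to the participants more than 20 % of participants". It names no arm, does not define harm, and does not say whether the percentage is of those enrolled so far, those treated, or all who are planned.

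The safety part of section 9 covers screening before consent, explanation and demonstration. After enrolment its one monitoring statement is that "the researcher will observe participants" for how they feel during assessment.

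Four other places bear on the point:
- Section 6.2.3, item 4, lets a participant who is uncomfortable leave at any session. It does not say that the reason is recorded or counted as harm.
- The primary and secondary outcomes in section 9 include no safety outcome, and the statistics part plans no safety summary.
- Sections 7 and 8 place much of the treatment outside assessment: mobilization twice a week for 4 weeks, plus home exercise with stretches listed three times a day.
- Section 6.3 gives the size: "the researcher will collect data from 24 shoulder impingement syndrome patients", with "12 subjects on the conventional group and 12 subjects on the mobilization with movement group".

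**The concern.** A percentage rule needs a definition of the event, a way of finding events, someone to count them at stated times, and a denominator. The protocol commits to the percentage, but the text available describes no process that produces the numerator. Discomfort after a session, or a flare during home exercise, would be noticed only if the participant happened to mention it. Two investigators could see the same events and disagree on whether the rule had been met.

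Two things are at stake. One is participant safety, because ending the project depends on this count. The other is the report: the trial compares conventional therapy with and without mobilization, and without harms recorded by arm it can say little about the harm side of that comparison. The wording also does not separate the arms, although only half the participants receive the added technique. Harm specific to that technique would be diluted about two-fold in a pooled percentage.

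**Working it through.** **Inputs.** Threshold: more than 20%, a strict inequality (section 6.2.4). Planned size: 24, 12 per arm (section 6.3). Calculated size before the dropout allowance: 20 (section 6.3).

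**The plan's own size.** Section 6.3 uses "mobilization with movement group was 4.6 (5.0) and that for the sham group was 0.4 (1.1"). The root-mean-square SD is √((5.0² + 1.1²)/2) = 3.62, so d = (4.6 − 0.4)/3.62 = 1.16. A two-sample t test at one-sided 0.05 needs 10 per arm for 80% power (80.2%), which matches "the total of this study equal 20 subjects". Sidedness and power are not stated, so both are assumptions. The dropout step reaches 24 as 20 × 1.2; dividing by 1 − 0.2 would give 25. Since 24 is what the plan will recruit, 24 is used below.

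**Where the rule stops the trial.** Find the smallest whole number k with k/N > 0.20. For N = 24, 0.20 × 24 = 4.8, so k = 5. The other rows show how the answer moves with the unstated denominator.

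| Reading of the denominator | Most harmed without stopping | First count that stops | If all harms are in the mobilization arm |
|---|---|---|---|
| All 24, pooled, full enrolment | 4/24 = 16.7% | 5/24 = 20.8% | 4/12 = 33.3% tolerated; 5/12 = 41.7% stops |
| 20, pooled (10 per arm) | 4/20 = 20.0% | 5/20 = 25.0% | 4/10 = 40% tolerated; 5/10 = 50% stops |
| First 4 treated, pooled | 0/4 | 1/4 = 25% | depends on how the 4 are split |
| Each arm of 12 separately | 2/12 = 16.7% | 3/12 = 25.0% | same as columns 2 and 3 |

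These rows show what the present wording can mean; none is recommended.

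**Chance of reaching the pooled count.** Assume, for illustration, no harm in the conventional arm and complete recording. With X ~ Binomial(12, p), the chance of 5 or more harmed by full enrolment is 0.37 at p = 1/3 and 0.61 at p = 5/12. The harm rates are assumptions; the documents give none.

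**What feeds the numerator.** The rule covers harm from the methodology at any time. The described monitoring covers assessment only. The described withdrawals are not tied to the rule. The weekly pain scores are not tied to it either.

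**The case against.** The strongest reply is that this is a routine completeness comment on a small, low-risk trial, and that harm is not invisible in it. Pain on the visual analogue scale is a primary outcome, compared between groups at weeks 1, 2, 3 and 4, and the disability index is compared at weeks 2 and 4. Worsening pain is therefore already measured by arm. Section 6.2.3 gives each participant an individual way out, and such withdrawals can be counted. The flow chart and the assessment form are not reproduced, so adverse-event handling could sit there.

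Much of this stands. A reader might infer that no adverse events are recorded at all, that the rule can never trigger, or that it is the plan's only protection for participants. The documents support none of these. They support only that no systematic recording is described, and that section 6.2.4 is a project-level rule beside the individual one in section 6.2.3.

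The arithmetic is also conditional. Pooling is the natural reading of a rule for the whole project, but it is not stated. Placing every harm in the mobilization arm is a chosen worst case, since both arms receive passive mobilization and strengthening work. On a running denominator, one harmed among the first four would already exceed 20%.

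The reply does not supply the missing count. No change in pain score is linked to the 20% rule, pain scores would miss other harms, and withdrawals for discomfort are not said to be recorded as such.

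**Conclusion.** The concern holds in a limited form. The protocol states a percentage rule for ending the project, but describes only observation during assessment to feed it, and plans no safety summary by arm. The rule cannot be applied reproducibly as written.

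The size depends on the reading. Three assumptions are needed: pooling over both arms, all 24 enrolled, and every harm in the mobilization arm. Under them the rule tolerates up to 4 of 12 (33%) in that arm and stops the trial at 5 of 12 (42%). A reader might take 42% as the level tolerated. It is not, because 5 of 24 is 20.8% and already above the limit. A tolerated level near 40% arises only if the denominator is 20.

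Asking for a definition of harm and a denominator is a request for missing detail. Recording events at every session is a concrete improvement on observation, and it supplies the count the rule needs. No efficacy estimate or test changes, so this is a worthwhile low-cost improvement and not a major flaw.

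**What to change.** At every session in both arms, ask whether any adverse event has occurred since the last visit, including increased pain and events during home exercise, and record the answer. Use the same question and form in both arms so that the counts are comparable. When a participant leaves under item 4 of section 6.2.3, record the discomfort that led to it. Report the counts by arm in one descriptive table; no test is needed.

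The investigators and the ethics board should reconcile sections 6.2.3 and 6.2.4 with the safety part of section 9, stating what counts as harm and what the 20% is a percentage of. No threshold is proposed here.

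The cost is one line on the visit form and one table.

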## **6.2.5 Subject allocation** (for more than 1 arm study)

The participants will be allocated into 2 groups according to age allocation and will be randomized by sealed envelopes.

### 6.3 Sample size

Sample size calculation will be performed using formula for the test of different between 2 independent means.

According to the G\*power 3.1.9.2 program calculation, the total of this study equal 20 subjects. Based on the previous study using the shoulder pain and disability index to measure the shoulder function, in the study of comparing the immediate effects of mobilization with movement and sham techniques. The mean (standard deviation) between group post-intervention for the mobilization with movement group was 4.6 (5.0) and that for the sham group was 0.4 (1.1) (12). In this proposed study, we need equal number of participants per group; therefore, the drop out calculation of 20% from the total participants (n = 1/1-20%). Therefore, after the ethical approval, the researcher will collect data from 24 shoulder impingement syndrome patients (12 subjects on the conventional group and 12 subjects on the mobilization with movement group).

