## 6.4 Replacement procedure if subject withdraw from the study

not necessary because the number of subjects calculated already include drop out number

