## - Statistics to be used or process for data analysis

Data will be analysed by using SPSS version 23. The statistical significance level is set at p-value < 0.05.

- Shapiro-Wilk will be used to examine the distribution of the data
- Descriptive statistics for demographic data, mean and standard deviation for continuous, cumulative frequency for categorical and median for ordinal variables, will be calculated.
- Two-way mixed design ANOVA (two group x four time) for parametric data. If the data are significant the post hoc analysis will be performed using Bonferroni.
- Friedman test if the data are not normally distributed.

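### Enrolling 24 does not cover the stated 20% dropout: the plan's formula gives 25 (26 for equal groups), so the reason given for not replacing withdrawals fails at that rate

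*Combined protocol and SAP*

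**What the plan says.** All of this is in the combined protocol and SAP.

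- Section 6.3, number needed: "the total of this study equal 20 subjects".
- Section 6.3, balance: "we need equal number of participants per group".
- Section 6.3, allowance: "the drop out calculation of 20% from the total participants (n = 1/1-20" per cent.
- Section 6.3, enrolment: "the researcher will collect data from 24 shoulder impingement syndrome patients", split as "12 subjects on the conventional group and 12 subjects on the mobilization with movement group".
- Section 6.4, on replacing withdrawals: "not necessary because the number of subjects calculated already include drop out number".

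The figures behind the 20 are the means and SDs taken from an earlier trial, "between group post-intervention for the mobilization with movement group was 4.6 (5.0) and that for the sham group was 0.4 (1.1"). Section 9 sets the significance level: "The statistical significance level is set at p-value < 0.05". Section 6.3 does not give the power, whether the test is one- or two-sided, or how the two unequal SDs were combined.

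**The concern.** A dropout allowance is meant to leave the required number after the assumed loss. Dividing by one minus the dropout rate does this; multiplying by one plus the rate falls short, because the loss then applies to a larger number than the one it was computed from. Section 6.3 prints a formula of the first kind and a total of the second.

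This matters beyond the arithmetic because section 6.4 relies on the total. It says replacement is unnecessary on the ground that dropout is already counted. If 24 does not absorb 20% loss, the plan expects fewer subjects than it says it needs and has no stated way to make up the difference.

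**Working it through.** **Inputs.** Required total 20, dropout 20%, equal groups and enrolment 24 (12 + 12), all from section 6.3. Significance level 0.05 from section 9.

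**Where 24 comes from.** 20 × (1 + 0.20) = 24. This reproduces the stated total exactly.

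**What the printed formula gives.** The formula appears without brackets, which may be lost layout, so it is read as 1/(1 − 20%):

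- total: 20/(1 − 0.20) = 25
- per group: 10/(1 − 0.20) = 12.5, rounded up to 13, so 26 in total with equal groups

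**What 24 covers.**

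- expected completers at 20% loss: 24 × 0.80 = 19.2 (9.6 per group), which is 0.8 below 20
- largest loss that still leaves 20: 24 − 20 = 4, and 4/24 = 16.7%

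**Chance of keeping the target.** This assumes each participant is lost independently with probability 0.20 (binomial).

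| Enrolled | P(at least 20 remain) | P(at least 10 remain in each group) |
|---|---|---|
| 24 (12 + 12) | 0.460 | 0.558² = 0.312 |
| 25 | 0.617 | – |
| 26 (13 + 13) | 0.747 | 0.747² = 0.558 |

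**Cost in power.** The difference in means is 4.6 − 0.4 = 4.2. Two ways of combining the SDs were tried:

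- pooled: √((5.0² + 1.1²)/2) = √13.105 = 3.620, so d = 4.2/3.620 = 1.160
- simple average: (5.0 + 1.1)/2 = 3.05, so d = 4.2/3.05 = 1.377

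Power comes from the noncentral t distribution with n₁ + n₂ − 2 degrees of freedom and noncentrality d/√(1/n₁ + 1/n₂), at alpha 0.05. Three combinations give 20 as the smallest equal-group total. Sidedness and target power are assumptions here.

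| Assumptions that give 20 | Power, 10 + 10 | Power, 10 + 9 | Loss, points |
|---|---|---|---|
| pooled SD, one-sided, 80% target | 0.802 | 0.782 | 2.0 |
| average SD, two-sided, 80% target | 0.829 | 0.806 | 2.3 |
| average SD, one-sided, 90% target | 0.906 | 0.891 | 1.5 |

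The inputs do not show which of these was used, and nothing here says that 20 is wrong. The figures are for a t-test at one time point, not for the mixed-design ANOVA planned in section 9.

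**The case against.** The best defence is that the words of section 6.3, taken without the formula, can mean adding 20% of 20. That gives exactly 24 and an allowance of 4 people, and section 6.4 is then correct that a dropout number is included. This reading is possible and probably explains the 24. It does not rescue the text: the formula in the same sentence divides by one minus 20% and gives 25, so wording and formula disagree. A 20% loss among those enrolled still leaves 19.2. The defence works only if the dropout rate is defined as a share of the 20 who finish, which the formula contradicts.

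The second objection is that the effect is close to nothing, and that is largely right. The gap is one or two patients. With the average SD and a two-sided test, 10 + 9 still gives 0.806, above 80%. The 20% is itself a planning guess for which the document gives no basis.

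Third, the binomial figures should not be over-read. Dividing by one minus the rate aims at the expected number and guarantees nothing: even 25 keeps 20 or more only 62% of the time. At a true loss of 16.7%, 24 keeps 20 or more about 63% of the time. Much of the shortfall in those probabilities is chance variation rather than the arithmetic slip.

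Finally, section 6.4 calls replacement unnecessary; it does not forbid it. What fails is the reason it gives.

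**Conclusion.** The point holds and is minor. With 20 required and a 20% allowance, the plan's own formula gives 25, or 26 for equal groups, against 24 stated. Twenty-four absorbs a loss of 16.7%, so the justification in section 6.4 is sound up to four withdrawals and fails at the stated rate. The shortfall is 1 to 2 patients enrolled, or 0.8 of an expected completer.

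The conclusion takes 20 as given and reads the dropout rate as a share of those enrolled, as the formula implies. It does not depend on how the 20 was derived. Only the power cost of 1.5 to 2.3 points does, and it rests on the assumed sidedness, target power and SD rule shown above.

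**What to change.** Keep 24 and correct the claim made for it.

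In section 6.3, replace the 20% and the formula with:

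> Enrolment will be 24 (12 per group). This allows for the loss of 4 (16.7%) to leave 20; at 20% loss about 19 completers are expected.

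In section 6.4, replace the reason with:

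> Withdrawn participants will not be replaced; enrolment of 24 allows for the loss of 4 (16.7%).

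The cost is two changes of wording, with no added patients, visits or measurements. The one downside is that the stated allowance falls from 20% to 16.7%. If the sponsor prefers to keep a 20% allowance with equal groups, the matching total is 26 (13 per group), at the cost of two more patients.

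As a separate reporting addition, section 6.3 could state the power, sidedness, SD rule and effect size entered in the program, and say whether 4.6 and 0.4 are changes or scores. The correction above does not depend on it.

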## 6.4 Replacement procedure if subject withdraw from the study

not necessary because the number of subjects calculated already include drop out number

#### 7. Study procedures

## Assessment

1. Scapulohumeral rhythm on shoulder abduction: there should be no reverse scapulohumeral rhythm, scapular tracking will be assessed for defining the scapular motion abnormalities and glenoid rotation on the scapular abduction. If there is a presence of scapular abnormalities the patients will be assessed on the point 2 and 3.

MU-CIRB	Mahidol University Central Institutional Review Board (MU-CIRB)	Date Modified 02/08/2016
Mahidol University Centra	l Institutional Review Board (MU Central-IRB) Study Protocol	Page 6 of 13

[figure not shown]
- 2. Scapular dyskinesis test of McClure: active shoulder flexion and abduction using 1 kg dumbbells on both hand flexion and abduction while the therapist will assess the scapular motion from behind, the result of scapular winging, shrugging or tipping will define the conventional treatment for each patient.
- 3. Scapula assistance test: during shoulder abduction elevation the therapist will assist the scapular movement at the inferior angle of the shoulder blade to see which stabilizer muscles have weakness.
- 4. Painful arc: the pain is occurring during 60-120 degrees of shoulder abduction elevation.
- 5. External rotation test: known as Infraspinatus test, the patient will perform isometric contraction of shoulder external rotation in neutral shoulder abduction.
- 6. Empty can test: during 90 degrees of shoulder abduction and maximally internal rotation, the test is isometric abduction while the therapist hand will resist the patient's hand.
- 7. Drop arm test: during 90 degrees of shoulder abduction, the therapist hand will support the patient's elbow. Next, the therapist will move the support and ask the patient to lowering the hand slowly to test the eccentric performance.
- 8. Lift off test: known as Subscapularis test, the patients will place their hand resting in middle lumbar region and perform the extension or lift the hand and reach to the back as far as they can.
- 9. Scapular retraction test: the therapist will support the scapula to retract while the will patient performs the empty can test. If the pain is reduced while performing the test, it means that the source of the pain is from the weakness of scapular stabilizer muscle only.

# Research Equipment

### 1. Visual analogue scale

The pain will be measured during the shoulder abduction because the provocation of the impinged structure is high on the range of 60 to 120 degrees.

The therapist will ask the patient to rate the pain on the VAS scale from 0 to 10.

## 2. Bubble inclinometer (Baseline, USA)

The therapist will put the inclinometer on the upper arm and set the marker to the edge of the bubble. The patient will perform shoulder abduction on standing position, internal rotation and external rotation on the supine position with 90 degrees shoulder abduction and elbow flexion.

[figure not shown]
# 3. Canon EOS M 10 (Canon. Japan) and tripod

The camera and tripod will be set up on the postural assessment room, the range of the tripod and camera will be set on maximum zoom and 4 meters from the patient. The height of the tripod will be adjusted depending on the patient's height ranging from 130 to 150 cm.

### 4. Postural assessment software (SAPO ver. 0.69 BMC Brazil)

The therapist will ask the patient to stand beside the grid line and face the marker on the wall. The results of the photograph will be inputted to the software and the examiner will mark the degree of cervical angle and sagittal shoulder posture.

MU-CIRB	Mahidol University Central Institutional Review Board (MU-CIRB)	Date Modified 02/08/2016
Mahidol University Centra	ll Institutional Review Board (MU Central-IRB) Study Protocol	Page 8 of 13

# 5. Hand held dynamometer (Micro FET2, Hoggan. USA)

The therapist will place the dynamometer on the arm and ask the patient to push against the therapist's hand to test the isometric contraction prior to each muscle. The test is performed to measure abductor and external rotator muscles.

# 6. Shoulder pain and disability index (SPADI) questionnaire

The therapist will ask the patient to rate the pain and shoulder disability on the SPADI questioner, the therapist will explain how to rate and measure the score. If the patient does not understand the question, the examiner will help until the patient can understand.

#### Flow chart of procedure

MU-CIRB	Mahidol University Central Institutional Review Board (MU-CIRB)	Date Modified 02/08/2016
Mahidol University Centra	l Institutional Review Board (MU Central-IRB) Study Protocol	Page 11 of 13

